### Conceptual model of barriers to change.

Addressing this weakness, we and others have begun demonstrating that such affective (i.e., automatic) feeling states are the primary motivational factors driving humans to engage in physical activity. Furthermore, these motivational factors have highly transient effects, exhibiting more state than trait qualities. Our team developed the Wants and Aversions for Neuromuscular Tasks (WANT) model to explain these relationships based on Kavanaugh's model of affective motivation states determined by motive states, affective valence (pleasure/displeasure), and arousal/activation. Past models by contrast have relied exclusively on social cognitive theory (SCT) constructs (i.e., self-efficacy, outcome expectations, sociocultural traits). Therefore, we must test not only SCT constructs but also WANT model real-time states to link T1D-related barriers to physical activity (Figure 2).

In sum, our secondary objectives will address underlying psychological mechanisms of the intervention. Knowledge of these mechanisms would improve tailoring. For example, if we find an individual's lack of motivation for physical activity is predicted by having below-average starting blood glucose, a below-average blood glucose reading an hour before opportunities for physical activity would trigger a reminder for additional carbohydrates. On the other hand, if we find the predictor is *fear* of hypoglycemia, the message would provide psychological support such as cognitive behavioral therapy for fear of hypoglycemia. To generate the needed mechanistic knowledge, we have proposed the secondary aims of this study.

**Figure 2.** Hypothesized conceptual model of factors influencing physical activity behavior change. Dotted lines indicate alternative hypothesis that T1D-related barriers directly impact physical activity without mediation by motivation states.

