# 1.2.3. We can use data from momentary surveys and continuous biometric monitoring to predict physical activity among adults with T1D.

Using data from the above study with adults (c.f sect 1.2.1, 1,125 person-days), we developed a deep neural network to predict the successful completion of physical activity on each day (≥10min sustained) using 95 possible predictive features derived from the prior 7 days of state fear of hypoglycemia, sleep quality, blood glucose variation, and demographics. The method showed promise to predict physical activity for the adults with T1D (80% accuracy, 82% precision, 85% sensitivity, 74% specificity). The secondary objectives of the current study will use our newfound WANT model to elucidate psychological mechanisms of T1D physical activity, thus increasing success of prediction. We have evidence from the general population that higher want for physical activity is associated with 8%-19% greater odds of current or intended physical activity.

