They will also be provided a comprehensive exercise safety orientation which is detailed in Appendix 22a. Briefly, the information includes review of devices, supplies, space, safe glucose ranges and carbohydrate snacking for exercise, reminders from CGM training pertinent to exercise, insulin adjustments around exercise, watching for symptoms, and who to call with concerns. They will be provided and instructed to keep carbohydrate-containing foods and drinks (eg, orange juice, glucose tablets) available to use when indicated by glucose testing or symptoms. In addition, they will be educated regarding the American Diabetes Association guidelines for self-monitoring blood glucose and urine ketones, if indicated, and appropriate adjustments of diet and insulin before, during, and after engaging in exercise. For instance, if blood glucose is less than 90 mg/dL, they can consume 10-20g of fast-acting carbohydrates (eg, 4 oz of orange juice or 3 glucose tablets) and wait to commence with exercise until blood glucose is confirmed to be above 90 mg/dL. If blood glucose is greater

Protocol Number 2000035846

August 13, 2024 Version #7

than 270 mg/dL and not associated with a recent meal, they must check their blood for ketones and avoid exercise if they have ketones ≥1.0 mmol/L.

Participants will be encouraged to be vigilant for symptoms of hypoglycemia during exercise and for the remainder of the day because exercise increases the risk for nocturnal hypoglycemia. The symptoms they will be encouraged to be vigilant for include cold, clammy skin, pallor, difficulty concentrating, shakiness, lack of coordination, irritability, hostility, and poor behavior, a staggering gait, fatigue, nervousness, excessive hunger, headache, blurred vision and dizziness, and abdominal pain or nausea. In these instances, they will be advised to refrain from exercise while checking blood glucose.

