# STUDY PROTOCOL

# **Social Behavioral Template**

#### 6.1.1 Data Collection

#### STUDY DESIGN OVERVIEW

The study is a single-group longitudinal study with periods of familiarization with devices, intervention using devices and mobile app, and maintenance follow-up (Figure 4). The primary aim is observing the intervention for feasibility, acceptability, and mathematical robustness. The secondary aim is observing psychological and biometric outcomes through assessments (Table 2) which are completed 1x/weekly during the entire study to test long-term effects (hypothesis 2-1-2 & 2-2-1) and 5x/daily during maintenance follow-up to test momentary effects (hypothesis 2-1-1 & 2-2-2). The secondary aim also includes an interview at the end of the study (hypothesis 2-3).

**Figure 4.** Individual participant timeline. Blue indicates measures for primary aims and red indicates measures for secondary aims.

Table 2. Surveys used for secondary aims. Appendix has instruments for dependent variable (#2a,2b), independent

variables fear of hypoglycemia (#3a, 3b), exercise self	-efficacy (#4), exercise self-regulation (#	
valence (#6), daily intention and competing demands  PHASE	Momentary	Weekly
	(Hypotheses 2-1-1, 2-2-2) (Timepoints T1-T2)	(Hypotheses 2-1-2, 2-2-1) (Timepoints T0-T2)
ASSESSMENT SCHEDULE	5x daily at random times within 3hr bins under ambulatory conditions of daily living	Weekly in controlled setting (tele-video in quiet room)
DEPENDENT VARIABLE††		
Cravings for Rest and Volitional Energy Expenditure (CRAVE) survey of motivation states for physical activity*	Score of 1-item want "right now" and 1-item aversion "right now"	Score of 5-item want "past week" and 5-item aversion "past week"
INDEPENDENT VARIABLES		
Fear of hypoglycemia†	Score of 1-item "next 3 hours" version	Weekly score of 18-item "past week" version
Fear of hyperglycemia ††	Score of 1-item "next 3 hours" version	Weekly score of 24-item "past week" version
Blood glucose metrics‡	Past 3 hours averages and slope	Weekly averages
Exercise self-efficacy 	N/A	Weekly score of 9-item "past week" version
Exercise self-regulation 	N/A	Weekly score 15-item "past week" version
COVARIATES		
Non-T1D-related affective valence states previously associated with CRAVE score (pleasure/displeasure  , activation/arousal  ).§	Score of 1-item "right now" versions	Weekly score of 1-item "past week" versions
Day of week, time of day	Timestamp	N/A

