#### 7.2.1 Secondary Objective Analyses (if applicable)

All statistical models for secondary objectives 1 and 2 will estimate intraclass correlation coefficient (ICC) to assess the proportion of variance explained by participant ID.

Secondary Objective 1 (STATISTICAL, MULTILEVEL MODELING). Examine whether recognized T1D-related physical activity barriers (fear of hypoglycemia, glycemic variation) predict momentary and long-term variation in motivation states for physical activity

**Hypothesis 2-1-1. Momentary predictors of motivation states.** We will develop two multilevel models for the dependent variables of want and aversion for physical activity (CRAVE 2-item "right now") respectively. The independent variables and covariates (Table 2) will be separated into momentary states for level 1, daily states for level 2, and demographics for level 3.

Hypothesis 2-1-2. Week-to-week changes in motivation states. We will develop two generalized linear mixed models for the dependent variables of want and aversion for physical activity (CRAVE 10-item "right now") respectively. A random intercept will incorporate correlations within-subject. We will include long-term assessed independent variables and covariates (Table 2, last column) along with a time categorical variable to estimate the contribution of changes coinciding with intervention (T0 to T1) and maintenance follow-up (T1 to T2).

Secondary Objective 2 (STATISTICAL, MULTILEVEL MODELING). Examine whether motivation states for physical activity predict momentary and long-term variation in physical activity behavior change, adherence, and maintenance resulting from a T1D motivational physical activity intervention.

August 13, 2024

Version #7

Hypothesis 2-2-1 – Predictors of physical activity behavior change and adherence over the intervention. We will develop a generalized linear mixed model for physical activity behavior testing WANT and SCT constructs as independent variables. A random intercept will incorporate correlation within-subject. We will include long-term assessed independent variables and covariates (Table 2, last column) along with a time categorical variable to estimate the contribution of changes from intervention (T0-T1) and maintenance follow-up (T1-T2).

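### Hypotheses 2-1-1 and 2-1-2 are modelled only with adjustment for same-survey pleasure and arousal, which removes any glucose or fear effect that passes through current affect

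*Combined protocol and SAP*

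**What the plan says.** Section 1.1 (Conceptual model of barriers to change) bases the WANT framework on a "model of affective motivation states determined by motive states, affective valence (pleasure/displeasure), and arousal/activation". Affect is thus placed upstream of the outcome.

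Table 2 in section 6.1.1 gives affect a different role. Under covariates it lists "Non-T1D-related affective valence states previously associated with CRAVE score", meaning pleasure/displeasure and activation/arousal. In the momentary survey these are single items about the present moment, answered alongside the present-moment want and aversion items. In the weekly survey they are single items about the past week, answered in the same sitting as the weekly want and aversion scores.

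Section 7.2.1 puts everything in one model for 2-1-1: "The independent variables and covariates (Table 2) will be separated into momentary states for level 1". The model for 2-1-2 likewise takes the weekly independent variables and covariates together. Unadjusted as well as adjusted estimates are promised only for Hypothesis 2-2-2.

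Two places bear on whether glucose can change affect. Section 1.1 says glycemic destabilization causes intense symptoms that acutely preclude activity. Section 2.2 (Hypoglycemia) lists symptoms that include "fatigue, nervousness, excessive hunger, headache, blurred vision and dizziness".

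**The concern.** If low or falling glucose, or fear of hypoglycemia, makes a person feel worse, and feeling worse lowers the want to move, then affect lies on the path from predictor to outcome. Holding it fixed leaves only the part of the effect that bypasses it. A predictor that works mainly by making people feel bad would look weak in the planned model.

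This matters because the Synopsis gives the secondary purpose as finding mechanisms, and section 1.1 would use the answer to decide whether a later version of the app responds to glucose or to fear. Hypothesis 2-1-1 is also the only secondary hypothesis for which section 7.1 claims power.

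The label saying that these states are unrelated to T1D does not settle the matter. A single general rating of how one feels cannot separate displeasure caused by glucose from displeasure with another cause.

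**Working it through.** **1. The plan's own power figure.** Section 7.1 gives 21 completers × 50 observations = 1,050, ICC .28/.39 (want/aversion), total variances 9.9/12.3, design effects 14.21/20.11, standard errors 0.37/0.48, and 91%/81% power for a correlation of at least .34, naming pleasure and fear of hypoglycemia as examples.

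- Design effect = 1 + (50 − 1) × ICC: 1 + 49 × .28 = 14.72 (printed as 14.21) and 1 + 49 × .39 = 20.11.
- Standard error = √(variance × design effect / 1,050): √(9.9 × 14.21 / 1,050) = 0.366 and √(12.3 × 20.11 / 1,050) = 0.485.
- Effective n = 1,050 / 14.21 = 73.9 and 1,050 / 20.11 = 52.2. Fisher's z with r = .34 gives 90.9%/79.9% at one-sided 5% and 84.6%/70.0% at two-sided 5%.

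The stated power is thus reproduced to within about one point on a one-sided test; section 7.1 does not state sidedness. No term in this calculation allows for adjustment by a covariate correlated with the predictor.

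**2. Illustration of the attenuation.** Let r be the correlation of the predictor with the outcome and also of affect with the outcome, both set to .34 as in section 7.1. Let ρ be the predictor-affect correlation, which the documents do not give. The adjusted standardized coefficient is (r − rρ)/(1 − ρ²) = .34/(1 + ρ).

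| ρ (assumed) | Adjusted coefficient | Reduction, ρ/(1 + ρ) |
|---|---|---|
| 0 | .34 | 0% |
| .2 | .34/1.2 = .28 | 17% |
| .3 | .34/1.3 = .26 | 23% |
| .5 | .34/1.5 = .23 | 33% |

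**3. Mediator or confounder.** If a share s of a total effect of .34 runs through affect, the adjusted coefficient is .34 × (1 − s). A random-intercept simulation (21 people × 50 observations, person variance .28, ρ = .5, 60 replicates per case) agrees. For s = 0, 25, 50, 75 and 100%, the model without affect returned about .34 throughout, and the model with affect returned .34, .25, .17, .08 and .00. When affect was instead made a common cause of predictor and outcome, the adjusted model returned .34, .25, .16, .08 and .00. Ratings from one occasion therefore cannot tell the two structures apart.

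**4. Affect from the previous prompt.** Prompts fall at random within adjacent 3-hour windows (section 6.1.1, Visit 8). The gap between two successive prompts is then symmetric about 3 hours, so about half of previous prompts lie inside the 3-hour glucose window of Table 2. The first of the five daily prompts has no same-day predecessor. At 83% completion (section 7.1), and assuming that prompts are missed independently, the usable share is .80 × .83 = .66, a loss of about one third.

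**The case against.** The strongest reply is that the adjustment is deliberate and sound. Fear and affect are both self-reported at the same prompt, so low mood may raise reported fear and lower want. A fear-specific message needs fear separated from general mood, and a model without affect could then credit fear with an effect of mood. This stands for fear, and step 3 shows that the data cannot rule it out. It supports showing the adjusted model, but not showing it alone. It is weaker for momentary sensor glucose, which covers the 3 hours before the rating and is not self-reported. In the weekly model the ordering is looser, because the affect item and the glucose averages cover the same week.

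Other tempting readings go beyond the documents:

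- A reader might infer that the protocol itself states a route from glucose or fear through affect to motivation. It states only the second step. The first is inferred from the symptom descriptions in sections 1.1 and 2.2, and Table 2 assumes the opposite. The Figure 2 caption speaks of mediation by motivation states, not by affect.
- A reader might infer a definite loss of power for 2-1-1. The answer depends on the variance model. With the printed standard errors, an effect of .10 SD has only about 13%/11% two-sided power even without affect adjustment (.10 × √9.9 / 0.37 = 0.85; .10 × √12.3 / 0.48 = 0.73). A within-person regression on 21 × 50 prompts keeps essentially 100% power for r = .34 after adjustment. No single power loss can be quoted.
- A reader might infer a certain bias towards no effect. The mediated share is unknown, and pleasure and arousal could act in opposite directions.
- A reader might extend the point to weekly intention as a covariate in 2-2-1, because section 1.2.3 reports that "higher want for physical activity is associated with 8%-19% greater odds of current or intended physical activity". That is an association and gives no direction.
- Talk of a false null does not fit 2-1-2, for which section 7.1 plans effect sizes, not significance tests.

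**Conclusion.** The concern holds in a limited form. The only models stated for 2-1-1 and 2-1-2 condition on affect rated in the same survey as the outcome, although the theory cited in section 1.1 says affect determines that outcome. Whatever part of a glucose or fear effect passes through current affect is removed, and no companion estimate would show it.

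The size is unknown. The illustration (.34 falling to .28–.23) rests on setting both correlations to .34 and on an assumed ρ of .2 to .5. For fear, some or all of such a fall may be correct removal of confounding. Calling the attenuation a loss is better supported for sensor glucose, and there it rests on the plausible but unstated step from glucose to affect. The power in section 7.1 describes a marginal correlation and not the adjusted coefficient that the model would estimate.

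**What to change.** In section 7.2.1:

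- Report 2-1-1 and 2-1-2 both without and with same-occasion pleasure/displeasure and activation/arousal.
- For the sensor glucose predictors, name the model without concurrent affect as the total-effect estimate, and describe the adjusted model as the part not passing through affect.
- For self-reported fear, present the two models side by side and say that affect may be mediator or confounder.
- Optionally, for fear only, add a model adjusting for affect at the previous prompt of the same day, and state the loss of about one third of prompts. It is unsuitable for glucose because the previous prompt often falls inside the exposure window.

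In section 7.1, state that the power for a .34 correlation makes no allowance for adjustment for affect.

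While editing, reconcile the 2-1-2 outcome, which section 7.2.1 calls a right-now score and Table 2 a past-week score.

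The cost is wording and one extra model per outcome, with no new data. The drawback is that the fear estimate without affect may carry mood confounding, which is why it should not stand alone.

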### 1.2 Prior Experience (if applicable)

August 13, 2024 Version #7

# 1.2.1. Pilot study of mobile exercise support for middle-aged adults with T1D (Yale HIC #2000025992)

Working with an industry partner (GlucoseZone™, FitscriptLLC, New Haven, CT) we customized a mobile digital application providing on-demand instructional exercise videos, access to a text-based exercise coach ([name], an expert in T1D exercise), daily electronic self-monitoring diaries, and monthly reports of BG and exercise data discussed with [name] in a motivational enhancement therapy session. We evaluated its feasibility, safety, and acceptability in a pilot study. Participants were followed for 2 weeks of baseline and 10 weeks of application use and completed assessments by televideo that included wearable device setup, home-based clinical assessments, surveys, and interviews. Exercise was tracked by usage logs of the videos, electronic self-monitoring diaries for non-video guided exercise, and Apple Watch heart rate. All participants wore continuous glucose monitors (CGMs) and dispensed insulin by automated device (Bluetooth smartpen or continuous infusion pump); these data were captured by the "Share" feature of proprietary websites.

Recruitment. Using targeted Facebook news feed advertisements, word-of-mouth spread on Facebook and emails by role models with T1D, and approaching patients at clinical visits we recruited adults (N=20, 55% F, 42.3 $\pm$ 15.0 years old, 20.5 $\pm$ 15.3 years of T1D) with risk factors suggesting need for exercise intervention: body mass index 29.5 $\pm$ 5.1 kg/m², median 3 (IQR 0,7) daily exercise minutes, and high avoidance of exercise due to fear of hypoglycemia (3.9 $\pm$ 0.8 out of 5). News feed advertisements were more cost-effective than clinic recruitment (\$41.11 vs \$250.00 per eligible volunteer), captured higher-risk participants than role model word-of-mouth advertising (88% vs 25% obesity, 88% vs 25% elevated A1c), with faster yield than all other methods (8 participants enrolled over 20 days of advertising). Totally the eligibility rate was 20 / 47 = 43%.

Feasibility. Assessment completion was 85%-100% for all outcomes. Participants exercised with the app an average of  $2.4\pm1.7$  times per week and attended 35 / 40 monthly discussions (88%). Participants were queried on each non-exercise day about their barriers to exercise, and app malfunction was reported as a barrier <1% of the time. CGM data capture was  $92.5\pm7.2\%$  during baseline and  $88.3\pm9.8\%$  during weeks 9-10, with 95% of timepoints meeting literature standard  $\geq 75\%^{60}$ . Accelerometer wear time at baseline met the literature standard of  $\geq 10$  hours per day on  $6.7\pm0.6$  out of 7 days, with all participants above literature standard of  $\geq 4$  days per week, and accelerometer data at follow-up are pending analysis. Participants completed a median of 98% (IQR 88%, 100%) of the 84 possible mobile diaries, with 90% meeting literature standard  $\geq 70\%$ .

Safety. There were no episodes of ketoacidosis or severe hypoglycemia. Episodes of mild hypoglycemia were recorded on mobile diaries and reviewed by Drs. [name], [name], and [name] biweekly for safety concerns.

Acceptability. The overall intervention rating was moderate (3.4±0.9 out of 5). Participants rated the monthly feedback and coaching discussions most acceptable of all components (4.4±0.8 out of 5) but requested more frequent feedback and coaching sessions. The elements designed for more frequent touchpoints were rated somewhat lower (exercise videos 3.8±0.9, text-based exercise coach 3.2±0.8, daily diaries 2.2±0.6), *indicating need for more automated and frequent support as planned in the current study*.

Preliminary Efficacy. Participants increased their exercise from a median of 4 (IQR 0, 41) to 64 (20, 129) minutes per week (d= 0.71). Body mass index increased (d= 0.57). Systolic blood pressure (d= -0.45), HbA1c (d= -0.42), and mean sensor BG (d= -0.41) tended to slightly decrease while total daily insulin (d= 0.09) was not different. In summary, the intervention was safe and showed promising efficacy, *supporting virtually delivered exercise guidance if it can be delivered more intensively and sustainably*.

August 13, 2024 Version #7

### 1.2.2. Virtual exercise for other age groups with T1D

We have one clinical exercise trial for youth with T1D completed (Yale HIC #1605017843) and two in progress (#2000030105, #2000033736). The latter two occurred in virtual settings. These trials have had similarly high feasibility and acceptability as our adult study detailed above. None have had instances of severe hypoglycemia or diabetic ketoacidosis.

# 1.2.3. We can use data from momentary surveys and continuous biometric monitoring to predict physical activity among adults with T1D.

Using data from the above study with adults (c.f sect 1.2.1, 1,125 person-days), we developed a deep neural network to predict the successful completion of physical activity on each day (≥10min sustained) using 95 possible predictive features derived from the prior 7 days of state fear of hypoglycemia, sleep quality, blood glucose variation, and demographics. The method showed promise to predict physical activity for the adults with T1D (80% accuracy, 82% precision, 85% sensitivity, 74% specificity). The secondary objectives of the current study will use our newfound WANT model to elucidate psychological mechanisms of T1D physical activity, thus increasing success of prediction. We have evidence from the general population that higher want for physical activity is associated with 8%-19% greater odds of current or intended physical activity.

